7.1.1.1 Unadjusted analysis

CLR group

The CLR group is stratified by cluster size, i.e. number of participants per practice, as per the categories defined in the Milestone 1 review of the sample size (see Section 2.5.2): 50-65, 66-90, 91-125, 126-175, 176-225.

As a primary analysis, we will run a regression analysis based on individual-level data, followed by a secondary analysis based on cluster-level summaries to ensure that the conclusions are robust.

We will report on number of clusters and patients by stratum and study arm, and on the weighted average follow-up for the CLR group as shown in Section 2.5.4.

Individual-level data

We will first report on cumulative BE detection rate at one year (/ 1000 person-years) by stratum and study arm, and overall, using individual-level data. The one-year rate in the intervention arm will be estimated assuming a constant rate in the first four months and a (possibly different) constant rate thereafter (up to 18 months).

Primary endpoint data will be analysed by a mixed-effects Poisson regression for BE with fixed effects for the treatment and random effects to account for between-cluster variation (i.e. a random effect for the level of BE in each GP practice), with the number of person-years of follow-up as the offset. Additional fixed effect parameters will be included to account for strata (size of clusters in each stratum: 50-65, 66-90, 91-125, 126-175, 176-225).

The resulting 12-month rate ratio will be reported with 95% confidence interval and will be formally tested to see if it is significantly greater than 1.0 (with a two-sided alpha of 0.05).

To fit the Poisson regression random effects model to data, we will model the random effects using a log-gamma distribution.

In Stata, the `mepoisson` command performs a mixed-effects Poisson regression. See Section 11.2.1.1 of Hayes and Moulton for an explanation on the method. There will be two observations (and two durations of follow-up) for each patient: one for the first four months and a second thereafter. There will be a separate treatment effect for each period. The overall treatment effect will be calculated as the weighted mean of the two treatment effects using the Stata command `nlcom`.

Cluster-level data

As a secondary analysis, we will also analyse the data from the cluster-randomised practices using cluster level data. The analysis on cluster-level summaries will follow closely the method explained in Section 12.3.2 of Hayes and Moulton (see also Example 12.3 in the same textbook for a coding example in Stata in the case where the number of clusters (i.e. GP practices) in each stratum is balanced across study arms).

We will first report on mean BE detection rate (/ 1000 person-years) by stratum and study arm, and overall, using cluster-level data. As before, the cumulative rate at 12 months for the intervention arm will be estimated by dividing the follow-up into two periods: the first four months, and the subsequent follow-up (up to a maximum of 18 months).

By stratum: The rate ratio of BE detection for each stratum (approximate number of eligible patients in the practice) will be calculated as the exponential of the difference of the mean log(rates) for BE detection in the two study arms, which is equivalent to the ratio of the geometric means of the rates in the two arms for that stratum. 95% confidence intervals for stratum-specific RRs are calculated according to the method in Section 10.3.2.2 and Example 10.5 of Hayes and Moulton, using the number of clusters minus 2 as the degrees of freedom for the t distribution, the number of clusters per study arm, BE detection rates and standard deviations of cluster rates by study arm.

Overall: The overall estimate of the log rate-ratio will then be calculated as a weighted average of the stratum-specific estimates, with weights depending on the number of clusters per study arm and under the assumption that the between-cluster variance in log-rates within each combination of stratum and study arm is constant.

A *stratified t-test* will allow us to test the null hypothesis that the true rate ratio is 1 and to calculate the 95% confidence interval for the RR. The between-cluster variance for this test will be calculated as the residual mean square from the two-way analysis of variance of BE detection rate on stratum and study arm.

Sensitivity analyses will aim at substituting the empirical between-cluster variance with the following predefined values of ICC: 0.025, lower and upper bound of 50% confidence interval of empirical ICC.

Permutation test (on cluster-level summaries)

To check the validity of our inferences, we will use a permutation test. See Sections 6.2.1 and 10.6.3 of Hayes and Moulton on Restricted Randomisation and Permutation Test.

The stratified design of the CLR group implies that restricted randomisation was used in assigning each cluster to its study arm. Let N be the total number of clusters, M be the number of strata and $\{m_i \mid i = 1, \dots, M\}$ the size of the strata, so that $\sum_{i=1}^M m_i = N$. Then, if we require an equal number of clusters in the two study arms within each stratum, the number of possible allocations is:

$$\frac{m_1!}{\left(\frac{m_1}{2}\right)! \left(\frac{m_1}{2}\right)!} \times \dots \times \frac{m_M!}{\left(\frac{m_M}{2}\right)! \left(\frac{m_M}{2}\right)!}$$

assuming the number of clusters per stratum is even.

According to the strata chosen after the Milestone 1 review and the number and size of practices as of November 2018, this number should be roughly equal to 3×10^{19} , which is too large for the test to be computationally feasible (in a reasonable time). We will instead select a random sample of 5000 permutations. For each permutation, a t-test comparing BE detection rates between study arms will be performed. If the null hypothesis is true, then the observed effect measure can be regarded as having been randomly selected from this permutation distribution.

In Stata, this is done using the `permute` command.

PLR group

We will first report on the number of sites and patients per study arm, and average site size.

We will report on the weighted average follow-up for the PLR group as shown in Section 2.5.4.

Once again, the cumulative rate of BE diagnoses at 12 months will be estimated by dividing the follow-up into two periods: the first four months, and the subsequent follow-up (up to a maximum of 18 months).

A Poisson regression with BE detection rates / 1000 person-years as the outcome, study arm as the exposure and number of person-years as the offset will be run. The resulting rate ratio will be reported with 95% confidence interval.

Combined analysis (CLR + PLR group)

For the purposes of this analysis, the whole dataset will be considered. The same analysis as for the CLR group will be repeated (Poisson regression with random effects on individual-level data, stratified t-test on cluster-level data and permutation test), with the difference that the PLR group will represent a separate stratum of two clusters: one for patients randomised to the intervention and one for patients randomised to usual care. Note that the VIF for this cluster will be equal to 1 as we assume the ICC to be equal to 0: an ICC of 0 implies that there is no clustering so that individuals within the same cluster are no more similar than individuals from different clusters.

A weighted average follow-up will be calculated for the whole dataset as shown in Section 2.5.4. A further estimate of this will be made by considering only 6764 participants (in equivalent size terms) and we will check that this estimate is greater or equal than 12 months.

7.1.1.2 Adjusted analysis

Baseline data on age groups by sex, and length and dosage of acid suppressant medications are only available at practice level. The aggregated nature of the covariate data causes issues for the adjusted analysis both at individual level and at cluster level. For the latter, this is because adjustments for covariates are carried out with a two-stage procedure (see Section 12.3.2 of Hayes and Moulton) that, at first, relies on a regression model with individual-level data. Moreover, the aggregation of baseline data in PLR sites makes it impossible to separate intervention patients from usual care ones. Therefore, any adjusted analyses will not be possible for the primary endpoint.

7.1.1.3 Sensitivity analyses

As mentioned in Section 2.3, the primary endpoint analysis will be reiterated including also actual data on BE diagnoses in the intervention arm deriving from confirmatory trial endoscopies.

A further sensitivity analysis will impute possible additional cases of BE had all three data collection methods been used for all participants.

Moreover, in Section 3.2.2, we explained that three more sensitivity analyses will be performed on the per-protocol population to control for the fact that a number of patients have less than 6 months' worth of acid-suppressant medication prescriptions in the year preceding baseline.

7.1.2 Analysis of secondary endpoints

For the sake of simplicity, the cluster design of part of the Trial will be ignored for the analysis of secondary endpoints.

Any endpoints using data on BE diagnoses will rely on *actual* data available from the Trial, i.e. the methods used for data collection for the primary endpoint will not apply.

The analysis of the secondary endpoints will be further detailed in a separate supplementary SAP.

Using data from the intervention arm *only*:

- 1) Diagnostic accuracy of the Cytosponge™ according to endoscopic findings:
PPVs will be presented with 95% Clopper-Pearson (exact) confidence intervals overall, by age group/sex, by duration of acid-suppressant medication prescriptions prior to baseline and by number of columnal cells present on the sponge.
In Stata, these can be calculated using the command `diagt` or `diagti`. In R, the function `epi.tests` should be used.
- 2) Diagnostic accuracy of the Cytosponge™ test according to endoscopic and pathology findings, i.e. by score of BE severity:
PPV will be presented with a 95% exact confidence interval.
- 3) Performance of Cytosponge™ in detecting IM of the gastric cardia:
PPV will be presented with a 95% exact confidence interval.
- 4) Performance of Cytosponge™ in detecting BE or IM of the gastric cardia:
PPV will be presented with a 95% exact confidence interval.
- 5) Performance of Cytosponge™ in detecting EAC and gastric cancer:
PPV will be presented with a 95% exact confidence interval;
Numbers needed to examine (by Cytosponge™) to detect one OAC or one HGDB will also be calculated.
- 6) Sampling adequacy:
Inadequacy rate will be presented with a 95% exact confidence interval.
- 7) Endoscopy referral rates for adequate test results and successful Cytosponge™ swallows:
The two proportions will be presented with a 95% exact confidence interval.
- 8) Patient acceptability of Cytosponge™:
Proportions will be presented with a 95% exact confidence interval.
Median number of attempts to swallow per patient will be presented with interquartile range (IQR) and range.
At baseline:
 - Measures will be presented with median, IQR and range*At day 7-14:*
 - Measures will be presented with median, IQR and range
 - Differences in STAI-6 scores at day 7-14 and baseline will be compared with a Wilcoxon signed-rank test.
- 9) Physician/nurse acceptability of Cytosponge™: qualitative outcome.
- 10) Safety of Cytosponge™:

See Section 8.

11) Performance of repeat Cytosponge™ test:

Measures will be presented with a 95% exact confidence interval.

To be assessed using data from the usual care or both study arms:

12) Number of BE diagnoses missed in current management:

It will be estimated according to the following method.

Denote by B the number of cases of BE found and by N the numbers of participants in the denominator:

B_0 and N_0 refer to the numbers in the control arm (excluding the exit research endoscopies)

B_{01} and N_{01} refer to the numbers on the research endoscopies in the control arm

B_{11} and N_{11} refer to the numbers on the research endoscopies in the intervention arm (all Cytosponge™ negative at entry)

B_{10} and N_{10} refer to the numbers who did not have a Cytosponge™ in the intervention arm

N_{12} had a Cytosponge™ in the intervention arm with B_{12} BEs (excluding research endoscopies)

N_{13} had a positive Cytosponge™ and N_{14} had a subsequent endoscopy.

B_{14} had BE found via that endoscopy. B_{15} had BE found subsequent to the endoscopy (i.e. after a “negative” endoscopy). B_{16} had BE found following a positive Cytosponge™ despite not having endoscopy as a result of that positive.

The number of BE cases found by usual care is B_0 .

Among the N_{01} with a research endoscopy in the control arm, B_{01} cases of BE were missed under the current management. We need to calculate how many were missed in the $N_0 - N_{01}$ participants in the usual care arm without a research endoscopy.

First, consider how many BEs should have been found in the intervention arm had everyone been fully evaluated.

Had everyone with a positive Cytosponge™ had endoscopy, we estimate that $\frac{B_{14}}{N_{14}} N_{13}$ cases would have been found initially and $\frac{B_{15}}{N_{14}} N_{13}$

subsequently. The estimated total number of BE cases in those with a positive Cytosponge™ is:

$$T_1 = \frac{B_{14} + B_{15}}{N_{14}} N_{13} - B_{16}$$

The number of cases missed by Cytosponge™ could be estimated directly:

$$\frac{B_{11}}{N_{11}} (N_{12} - N_{13}).$$

But because N_{11} is (relatively) small, this number will be unstable.

Instead, we will use the sensitivity of the Cytosponge™ from BEST2 (80%) in those who did not have a research endoscopy. We then estimate a total of:

$$B_{11} + 0.25(B_{14} + B_{15}) \frac{N_{13}}{N_{14}} \times \frac{N_{12} - N_{13} - N_{11}}{N_{12} - N_{13}}$$

missed cases among those with a negative Cytosponge™. The estimated total number of cases in those with a negative Cytosponge™ is:

$$T_2 = (B_{12} - B_{14} - B_{15} - B_{16}) + B_{11} + 0.25T_1 \frac{N_{12} - N_{13} - N_{11}}{N_{12} - N_{13}}$$

Next, we need to consider how many cases would have been found in those having a Cytosponge™ had they been in the usual care arm. We

assume that those accepting a Cytosponge™ may not have the same rate as in those that did not accept. By subtraction, we estimate

$$T_3 = \frac{B_0}{N_0} (N_{10} + N_{12}) - B_{10}$$

cases among people accepting a Cytosponge™ (had they not been offered a Cytosponge™). So, among those using a Cytosponge™, BE was increased by the factor: $\frac{T_1+T_2}{T_3}$.

As in the intervention arm, we do not simply scale up from the research endoscopies in the control arm. Rather we combine the cases observed directly among those with a research endoscopy, by the expected number amongst the others using the intervention arm to scale up. The scale factor needed $R_0 = \frac{N_0 - N_{01}}{N_{10} + N_{12}}$, i.e. the numbers of people who did not get a research endoscopy in the control arm, divided by the total number in the intervention arm. The total number of cases in the intervention arm is made up of three parts: those observed by research endoscopy plus those in people who would have accepted the Cytosponge™, plus those among people who would not have accepted the Cytosponge™ is offered. The total is estimated as:

$$T_4 = B_{01} + (T_1 + T_2)R + \frac{T_1 + T_2}{T_3} B_{10}R$$

Hence the proportion of BE missed by current management is $\frac{T_4 - B_0}{T_4}$.

- 13) Number of undiagnosed BE in the general population vs in the group who received Cytosponge™:

The number of undiagnosed BEs in the patients who received the Cytosponge™ will be estimated by multiplying the proportion of BEs detected following a research endoscopy in the negative test group by the number of negative test patients.

The number of undiagnosed BEs in the usual care arm will be estimated by multiplying the proportion of BEs following a research endoscopy in the usual care arm by the number of patients in the usual care arm.

The two proportions of undiagnosed BEs will then be calculated out of the total number of patients in each of the two groups and will be compared using a chi-squared test.

- 14) Acceptability of endoscopy:

The proportion of participants in the usual care arm who attend their research endoscopy invitation will be compared to the proportion of participants in the intervention arm who attend their Cytosponge™ invitation using a chi-squared test.

- 15) Number of BE diagnoses for patients with a negative Cytosponge™ result:

Number of false negatives of the test arising from research endoscopies will be used to estimate the false omission rate, where we will use as denominator the number of negative Cytosponge™ patients who attend a research endoscopy invitation. The False Omission Rate will be reported with 95% confidence interval.

- 16) Quality control of endoscopic and pathology results:

For participants swallowing the Cytosponge™ successfully:

- Number (%) of BE diagnoses missed
- Number (%) of any other malignant diagnoses missed
- Number (%) of BEs falsely detected (if any)
- A “true” PPV for BE will be calculated and presented with 95% confidence interval.

For research endoscopies, usual care arm and negative Cytosponge™ patients separately:

- Number (%) of BE diagnoses missed
- Number (%) of any other malignant diagnoses missed
- Number (%) of BEs falsely detected (if any).

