4.1 Compliance to the Cytosponge™-TFF3 test

Compliance to test (intervention arm) will be defined on two aspects: attendance and successful swallows.

Participants will be provided with two opportunities to successfully swallow the device. A participant will be considered as having had the Cytosponge™ test if he or she has at least one successful swallow. Attenders will include patients who successfully swallow a sponge and those who present at their appointment but are not able to produce a successful swallow.

Study subjects successfully swallowing a Cytosponge™ may produce a sample deemed inadequate because of processing/technical failures or because the test result is considered to be low-confidence negative (squamous cells only) or equivocal (squamous and glandular cells with equivocal TFF3 staining). These patients will be invited to a repeat Cytosponge™ test.

The following numbers and proportions on compliance will feed into the Trial flowchart (see Figure 2):

- responders: overall, to first invitation letter only, to second invitation letter only
- interested and not interested (out of all responders)
- received screening phone call (out of interested): eligible, ineligible
- attenders and non-attenders/withdrawn (out of eligible)
- produced a successful swallow and unable to swallow (out of attenders)
- 'inadequate' samples (out of successful swallows) at first attempt and at repeat test: processing/technical failures, low-confidence negative (squamous cells only), equivocal (squamous and glandular cells with equivocal TFF3 staining)
- participants with 'inadequate' samples invited for a repeat test, attending the test, producing a successful swallow or unable to swallow
- 'adequate' samples (out of successful swallows) at first attempt, at repeat test, overall (i.e. only repeat test counts for participants having two tests) and in total (i.e. all tests counts): negative (squamous and glandular cells), low-confidence positive (squamous and glandular cells with IM), high-confidence positive (squamous and glandular cells with IM and cellular atypia)

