4.3 Compliance to research endoscopies (after end of follow-up)

Compliance to research endoscopies will be measured out of all patients receiving an invite to a research endoscopy. We will report on number of responders, interested/not interested, attenders and types of diagnoses both overall and by study arm.

Note: only participants in the usual care arm and patients receiving a negative Cytosponge™ test result were invited to a research endoscopy. A limited number of 'non-responders', i.e. patients who did not take up their Cytosponge™ invitation, were also invited to research endoscopies at the beginning of the rollout of this part of the trial; their invites were suspended shortly after. Despite the small figures, we will report on number of non-responders invited and attending a research endoscopy in the final statistical report.

5. Demographics and baseline characteristics

The following data will be available at baseline for each GP practice:

Usual care, intervention and PLR practices will send the study team the following baseline data in *aggregated* form (Excel spreadsheet see below):

- Number of participants enrolled by sex and age group
- Drugs administered and dosage

For PLR practices, the trial arm is not included in the aggregated baseline data.

Sex	Age bracket (yrs)					Total
	50-59	60-69	70-79	80-89	90-99	
Female						
Male						
Total						

Demographics and baseline characteristics will be presented by summary statistics. No statistical tests will be performed to compare these between study arms.

Number of sites, number of participants per study arm and average practice size will also be presented.

Patients who take up the Cytosponge™ invitation will have to complete the following CRFs, with the following information available to the Trial Statistician:

- Personal details CRF: sex, year of birth, ethnicity (sensitive data, available to the Statistician via the Trial Senior Research Application Programmer only)
- Allergies CRF
- Baseline Clinical CRF: height, weight, waist/hip circumference, medication for reflux symptoms and dose, gastro-oesophageal reflux disease impact scale questionnaire, heartburn start, H. Pylori, comorbidities
- Baseline Questionnaire CRF: education, smoking history, alcohol intake, risk perception, STAI 6 questionnaire, family history

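### Endpoint 13 sets undiagnosed BE to zero in Cytosponge-positive patients who did not have confirmatory endoscopy, although item 12 of the same section corrects for them

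*SAP*

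**What the plan says.** SAP section 7.1.2, item 13, describes its Cytosponge quantity in two parts:

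- Population: "The number of undiagnosed BEs in the patients who received the Cytosponge™ will be estimated by"
- Estimator: "multiplying the proportion of BEs detected following a research endoscopy in the negative test group by the number of negative test patients"

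The usual care quantity comes from "multiplying the proportion of BEs following a research endoscopy in the usual care arm by the number of patients in the usual care arm". Then: "The two proportions of undiagnosed BEs will then be calculated out of the total number of patients in each of the two groups", and the two are compared with a chi-squared test.

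Three other places bear on this.

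- Section 4.1 defines receipt of the test by swallowing, not by result: "A participant will be considered as having had the Cytosponge™ test if he or she has at least one successful swallow". The group therefore includes positives.
- Section 4.3 limits who could contribute research-endoscopy data: "only participants in the usual care arm and patients receiving a negative Cytosponge™ test result were invited to a research endoscopy" (apart from a few non-responders, whose invitations were suspended). Positives supply none.
- Item 12 of section 7.1.2 allows for positives without endoscopy. It writes N13 for positives and N14 for those who then had endoscopy, and begins "Had everyone with a positive Cytosponge™ had endoscopy, we estimate that", scaling BE up from N14 to N13. It also defines B15 (BE found after a negative endoscopy) and B16 (BE found in positives who did not have that endoscopy).

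**The concern.** The endpoint is meant to show how much BE remains undetected after each route of care. A positive patient who does not attend the confirmatory endoscopy is among the most likely to carry undiagnosed BE, and item 13 counts that patient as having none. The usual care figure is scaled up to every patient in the arm, so this omission has no counterpart there.

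False negatives are expected to be few, so the true Cytosponge figure is small. Even modest non-attendance among positives can then be a large share of it. Items 12 and 13 would also rest on inconsistent accounts of the same patients.

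**Working it through.** **Inputs from the SAP.** 13,234 participants (section 2.5.2), randomised 1:1 (section 2); uptake 24.0% (section 2.5.3); BE prevalence 4%, usual care referral 10%, BE among those referred 6%, sensitivity 85% (section 2.5.2); sensitivity 80% (section 7.1.2, item 12).

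**Assumed, not in the SAP.** Attendance at confirmatory endoscopy of 95%, 90% or 80%. I also take everyone who took up the test to have swallowed successfully with an adequate result, except in step 5.

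**1. Check of the inputs.** The SAP states no expected figure for endpoint 13, so I checked the inputs against its sample size. Intervention rate = 0.27 × [0.04 × 0.85 + 0.15 × 0.1 × 0.06] + 0.73 × 0.1 × 0.06 = 0.009423 + 0.00438 = 1.3803%, against 0.6%. With 90% power and two-sided 5%, this gives 6,764 in total, as the SAP states.

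**2. Patients tested.** 13,234 / 2 = 6,617; 6,617 × 0.24 = 1,588. BE among them: 1,588 × 0.04 = 63.5.

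**3. Omitted cases.** With sensitivity s and attendance a:

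- BE in positives = 63.5 × s; BE in negatives = 63.5 × (1 − s)
- item 13 counts 63.5 × (1 − s) only
- omitted = 63.5 × s × (1 − a)
- share omitted = omitted / (omitted + BE in negatives)

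| Sensitivity | BE in positives | BE in negatives | Omitted at a = 95% / 90% / 80% | Share omitted |
|---|---|---|---|---|
| 85% | 54.0 | 9.5 | 2.7 / 5.4 / 10.8 | 22% / 36% / 53% |
| 80% | 50.8 | 12.7 | 2.5 / 5.1 / 10.2 | 17% / 29% / 44% |

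At a = 100% the omission is zero.

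**4. Against usual care.** Undiagnosed BE in usual care = 4% − (10% × 6%) = 3.4%, or 34 per 1,000. Per 1,000 tested:

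| Sensitivity | Item 13 | With non-attending positives, a = 95% / 90% / 80% | Ratio to usual care: item 13, then corrected |
|---|---|---|---|
| 85% | 6.0 | 7.7 / 9.4 / 12.8 | 0.18, then 0.23 / 0.28 / 0.38 |
| 80% | 8.0 | 9.6 / 11.2 / 14.4 | 0.24, then 0.28 / 0.33 / 0.42 |

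**5. If inadequate results are also outside the negatives.** This applies only on one reading (see the objection). To avoid counting BE twice, the 4% is split over adequate and inadequate results. With an assumed 5% unresolved inadequate and 90% attendance at 85% sensitivity, per 1,000 tested:

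- item 13: 950 × 0.04 × 0.15 = 5.7
- positives without endoscopy: 950 × 0.04 × 0.85 × 0.10 = 3.2
- inadequate: 50 × 0.04 = 2.0
- total 10.9, ratio to usual care 0.32

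At 80% sensitivity the figures are 7.6 for item 13 and 12.6 in total. Over assumed non-attendance of 0–20% and inadequacy of 0–10%, the largest ratio to usual care is 0.50.

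**The case against.** **Inadequate results.** A reader might infer that patients whose result stayed inadequate are also set to zero. The SAP does not settle this. Item 12 uses N12 − N13, everyone tested who was not positive, as its negatives, and its direct estimate of missed cases has the same form as item 13. On that usage inadequate results are already scaled up, and an extra term would count them twice. Sections 2.3 (item 6) and 4.1 nevertheless class inadequate results apart from negatives. The term is ambiguous; the omission of positives stands on either reading.

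**Overall direction.** A reader might also infer that the whole comparison is biased towards the test. Only the omission has a known sign. The contrast sets self-selected acceptors against the whole usual care arm, and in item 12 the authors "assume that those accepting a Cytosponge™ may not have the same rate as in those that did not accept". That difference could act in either direction, so the net bias is not established.

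**Size.** The SAP gives no attendance rate, so every percentage above rests on an assumption, and the shares are smaller at item 12's 80% sensitivity. In no case tried does the Cytosponge figure reach that of usual care. All of this stands.

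**Visibility.** Section 4.2 reports attendance at confirmatory endoscopy separately, so non-attenders are not hidden from the reader. Section 7.1.2 also promises a supplementary SAP for the secondary endpoints. But item 13 already fixes its estimator, and reporting attendance elsewhere does not correct it. If the total number of patients meant test-negatives only, positives would drop out altogether and the result would no longer describe patients who received the test.

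**Conclusion.** The point holds for test-positives without confirmatory endoscopy. As written, item 13 understates undiagnosed BE in the Cytosponge group whenever attendance is incomplete and some non-attenders have BE that remains undiagnosed. It is inconsistent with item 12 on the same patients.

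For assumed attendance of 80–95%, the omission is about 17% to 53% of undiagnosed BE in positives plus negatives across the two sensitivities the SAP uses. It changes the size of the reported contrast rather than its likely direction. It concerns one secondary endpoint and leaves the primary analysis untouched. Whether inadequate results are also missed cannot be decided from the text.

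**What to change.** 1. Add to the Cytosponge numerator in item 13: [(B14 + B15)/N14 × (N13 − N14) − B16]. This is the BE expected in positives without endoscopy at the rate item 12 uses, less the cases already found in them.
2. State which patients item 13 counts as negative. If N12 − N13, inadequate results are included and no further term is needed; this takes the research-endoscopy proportion to apply to them. If adequate negatives only, add a term for unresolved inadequate results, with the prevalence chosen so that no BE is counted twice.
3. Describe the comparison with the whole usual care arm as non-randomised.

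The cost is a few sentences in the SAP or its promised supplement and a few lines of code. The quantities in step 1 are already defined in item 12; a count of unresolved inadequate results is not and would have to be added if step 2 calls for it. The reported Cytosponge figure will be less favourable if any non-attending positives are estimated to have undiagnosed BE.
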